10.6 Secondary Efficacy Variable Analysis

10.6.1 Rate and Time to Persistent AF/AT at 1 year and 2 years follow-up and at 3 years follow-up by number of ablations

For the secondary effectiveness endpoint, the rate and time to persistent AF/AT

(excluding isthmus dependent atrial flutter) at 1 year and 2 years, a KM analysis will be performed to examine the hazard function of persistent AF/AT (excluding isthmus dependent atrial flutter) for the two treatment groups at 1 year follow-up time and 2 year follow-up. Data will be censored at 1 year and 2 year follow-up (for subjects who are not censored earlier) in two separate analyses. The analyses will be performed on both the ITT and PP populations. Log-rank tests will be used to compare the hazard functions between the two groups at any observed event time. If observed, the median time to persistent AF/AT at 1 year and 2 year follow-up as well as the 95% confidence intervals will be reported by the two groups based on Kaplan-Meier estimates. The product limit estimates of the rate of survival without persistent AF/AT and the rate of persistent AF/AT at 1 year and 2 years follow-up as well as the 95% confidence intervals for the rates in the two groups will be presented.

A KM analysis will also be performed to examine the hazard function of persistent AF/AT (excluding isthmus dependent atrial flutter) at 3 years by number of ablations for the Test group. Number of ablations will be categorized into 1, 2, ≥ 3 ablations if sample sizes allow (otherwise, only categories for 1 and ≥ 2 ablations will be used). The median time to persistent AF/AT at 3 years follow-up as well as the 95% confidence intervals will be reported for the Test Group by the number of ablations. The product limit estimates of the rate of survival without persistent AF/AT and the rate of persistent AF/AT at 3 years follow-up as well as the 95% confidence intervals for the Test Group will also be presented by the number of ablations. The KM curves will be plotted and results will be listed as well.

These secondary efficacy variable analyses will also be repeated using the alternative definition of time to persistent AF (HRS 2017), as defined in section 8.3.

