### **11.2 Schedule of Examinations**

#### **11.2.1 Study Visits and Phone Follow-up**

Table 1 displays the required schedule for subject treatments and evaluations for Test and Control Groups. Sites participating in this study have been selected upon their capabilities to successfully carry out those assessments. Subjects will need to return to the hospital for a follow-up clinical visit at 3 months, 6 months, 1 year, 2 years and 3 years. Follow-up by phone will be conducted for all subjects at 9 months, 18 months and 30 months. Arrhythmia monitoring assessments, as described in Table 1, will be discontinued once subjects have progressed to persistent AF/AT.

All subjects will be followed through 3-years. Subjects who reach the primary endpoint (progress to persistent AF/AT) will only have to return for the final visit at 3 years; however, they will be followed for safety through the 3-years study period by their hospital and all adverse events are to be reported by the investigator as per protocol requirements. Subjects in the Test Group who undergo a repeat ablation procedure will continue follow-up according to the schedule of their index (first) ablation procedure. Thus, subject visits will be counted from the time of the index ablation procedure and not from the date of the repeat ablation procedure. Subjects in the Control Group who undergo an ablation procedure (cross-over), will continue follow-up according to their initial schedule.

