### **13.12 Secondary Effectiveness Endpoints Analyses**

#### **13.12.1 Rate and Time to Persistent AF/AT at 1 year, 2 and 3 years follow-up by number of ablations**

For the secondary effectiveness endpoint, the rate and time to persistent AF/AT (excluding isthmus dependent atrial flutter) at 1 year and 2 years and the rate of persistent AF/AT at 3 years by number of ablations, a KM analysis will be performed to examine the hazard function of persistent AF/AT (excluding isthmus dependent atrial flutter) for the two treatment groups at 1 year follow-up time and 2 year follow-up and 3 year follow-up in the Test Group by the number of ablations. Data will be censored at 1 year and 2 year follow-up in two separate analyses. The analysis will be performed in both the ITT and PP populations. A log-rank test will be used to compare the hazard functions between the two groups at any observed event time. The median time to persistent AF/AT at 1 year and 2 year follow-up as well as the 95% confidence intervals will be reported by the two groups. The survival probability and rate of persistent AF/AT at 1 year and 2 years follow-up as well as the 95% confidence intervals for the two groups will be presented.

The median time to persistent AF/AT at 3 years follow-up as well as the 95% confidence intervals will be reported for the Test Group by the number of ablations. The survival probability and rate of persistent AF/AT at 3 years follow-up as well as the 95% confidence intervals for the Test Group will also be presented by the number of ablations. The KM curves will be plotted and results will be listed as well.

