2.2 Efficacy, Safety and Health Economic Endpoints

2.2.1 Efficacy Endpoints

The primary efficacy endpoint is the time to persistent AF/AT (excluding isthmus-dependent atrial flutter) at 3 years. According to the protocol, persistent AF/AT is defined as AF/AT lasting longer than 7 consecutive days or requiring termination by cardioversion after 48 hours.

Secondary efficacy endpoints are:

- Rate and time to persistent AF/AT at 1 year and 2 years, rate of persistent AF/AT by number of ablations at 3 years
- Number of repeat ablations and new anti-arrhythmic drugs (AAD) per subject throughout 3 years follow-up

- Rhythm (% subjects in sinus rhythm (SR), % subjects with recurrent AF/AT) throughout 3 years follow-up
- Factors associated with AF disease progression
 - Gender
 - Age
 - Left atrium (LA) size
 - HATCH score (score based on the five components: Hypertension, Age 75 years or older, Previous transient ischemic attack or stroke, Chronic obstructive pulmonary disease, and Heart failure)
 - Blood pressure
 - NYHA functional classification of heart disease
 - Presence of diabetes
 - Presence of hyperlipidemia or dyslipidemia
 - Presence of renal insufficiency
 - Presence of dementia

In addition, an alternative definition of the primary and the first secondary endpoint will be investigated based on the consensus statement of the HRS (Heart Rhythm Society, 2017). According to the HRS consensus statement 2017, persistent AF/AT is defined as continuous AF/AT that is sustained beyond 7 days.

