7. ANALYSIS POPULATIONS

The following analysis populations will be used to complete the analyses of data.

Cross-over subjects will be handled differently for each type of analysis population, as described subsequently. In general, subjects from the control group who have an ablation procedure after the primary endpoint is met will not be analyzed as cross-over.

Intent to treat (ITT) population: The ITT subject population will include all

subjects randomized, where subjects will be classified by the group to which they are randomized, regardless of the treatment received. For the ITT population, cross-over subjects will be included in the Control Group per randomization. Lost-to-follow-up and withdrawn/early termination subjects will also be included in the ITT population.

Per protocol (PP) population: The PP subject population will include randomized subjects who satisfy the following criteria, according to the treatment actually received:

- **Test Group:** subjects who
 - have undergone RF ablation,
 - are treated with the study catheter (THERMOCOOL[®] Catheter Family),
 - are in compliance (no major protocol deviations that has an impact on scientific value of the study) with the study protocol, and
 - have been treated for the study-related arrhythmia.
- **Control Group:** subjects who
 - have started an investigator-prescribed AAD and completed the dose-loading period (2 weeks),
 - have not undergone RF ablation,
 - are in compliance (no major protocol deviations that have an impact on scientific value of the study) with the study protocol, and
 - have been treated for the study-related arrhythmia.

All analyses conducted in the PP population will be as treated analyses. For descriptive tables and simple inferential models with fixed treatment effects subjects who have undergone RF ablation will be included in the Test Group regardless of the original treatment assigned (original randomization). Thus, cross-over subjects will be included in the Test Group for PP analyses. For more complicated inferential analyses, models will be applied where treatment itself is included as time-dependent covariate (see section 10.2 and 10.6.4). The approach described above applies for all tables which do not summarize data by visit (e.g. for time to event endpoints and other endpoints calculated overall per-patient). For summaries by visit and repeated measurement models, cross-over subjects will be completely excluded.

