8.3 Derived Variables

Duration of AF [months]

Time between the recorded date of first AF and the date of randomization.

Time to persistent AF/AT

According to protocol, persistent AF/AT is defined as AF/AT lasting longer than 7 consecutive days or requiring termination by cardioversion after 48 hours. The primary endpoint is reached at the date of the first cardioversion after randomization (except cardioversion solely as part of a (re-)ablation procedure) or detection of persistent AF/AT by transtelephonic monitoring (TTM, performed between month 3 and month 36). The sponsor will review and adjudicate all events (progressions to persistent AF/AT), which were reported by the Investigator. Adjudication will already be performed for the interim analyses. All events where the sponsor confirmed in their final assessment that the primary endpoint was reached will be taken into account for analysis. The date at which the primary endpoint was reached will be taken as adjudicated by the sponsor or as reported by the Investigator (if no sponsor adjudicated date is available).

The protocol is not specific about the start date for time to event calculation. Originally according to SAP version 1.0 (which was applied for the interim analyses) time to event had been defined as the difference between randomization date and the date at which the endpoint was reached. However, after further discussion, it was decided to update the start date for time to event calculation for final analysis and to use date of procedure as start date for the test group, and date of randomization as start date for the control group.

This approach seems to be more appropriate and more conservative, as visit windows are calculated from date of procedure for test group. Otherwise, if time to event was calculated from date of randomization, test group would have longer follow-up period and longer time to each follow-up visit as control group.

If the primary endpoint is not observed during follow-up time, subjects will be regarded as censored at the completion visit/ last visit or at the last time TTM was recorded, whichever is later.

Time to persistent AF (HRS 2017)

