14.2 EFFICACY DATA				
14.2.1.1	ITT	Time to Persistent AF/AT (Primary Efficacy Analysis) Results of Kaplan-Meier analysis and log rank test	16.2.17.1	2.1 (but without rates at 3 years and incl. conditional power)
14.2.1.2	ITT	Time to Persistent AF/AT (Primary Efficacy Variable)	16.2.17.1	2.2

Table Number	Population	Table Title / Summary	Supporting Listing	Interim Analysis Number
		Recalculated Operating Characteristics for Group Sequential Design		
	ITT	Time to Persistent AF/AT (Primary Efficacy Variable) Sample Size Re-Estimation	16.2.17.1	2.3 Only required for first interim analysis; not required for final analysis
14.2.1.3	ITT	Time to Persistent AF (HRS 2017) Results of Kaplan-Meier analysis and log rank test	16.2.17.1	
14.2.2.1	PP	Time to Persistent AF/AT Results of Kaplan-Meier analysis and log rank test	16.2.17.1	
14.2.2.2	PP	Time to Persistent AF/AT Cox regression analysis including treatment as time-dependent covariate	16.2.17.1	
14.2.2.3	PP	Time to Persistent AF (HRS 2017) Results of Kaplan-Meier analysis and log rank test	16.2.17.1	
14.2.2.4	PP	Time to Persistent AF (HRS 2017) Cox regression analysis including treatment as time-dependent covariate	16.2.17.1	
14.2.3.1	ITT	Time to Persistent AF/AT: Subgroup analyses Results of Kaplan-Meier	16.2.17.1	

Table Number	Population	Table Title / Summary	Supporting Listing	Interim Analysis Number
		analysis		
14.2.3.2	ITT	Time to Persistent AF (HRS 2017): Subgroup analyses Results of Kaplan-Meier analysis	16.2.17.1	
14.2.4.1	ITT, PP	Time to Persistent AF/AT by Number of Repeat ablations Results of Kaplan-Meier analysis	16.2.17.1	
14.2.4.2	ITT, PP	Time to Persistent AF/AT at 1 Year Results of Kaplan-Meier analysis and log rank test	16.2.17.1	
14.2.4.3	ITT, PP	Time to Persistent AF/AT at 2 Years Results of Kaplan-Meier analysis and log rank test	16.2.17.1	
14.2.4.4	ITT, PP	Time to Persistent AF (HRS 2017) by Number of Repeat ablations Results of Kaplan-Meier analysis	16.2.17.1	
14.2.4.5	ITT, PP	Time to Persistent AF (HRS 2017) at 1 Year Results of Kaplan-Meier analysis and log rank test	16.2.17.1	
14.2.4.6	ITT, PP	Time to Persistent AF (HRS 2017) at 2 Years Results of Kaplan-Meier analysis and log rank test	16.2.17.1	
14.2.5	ITT, PP	Number of Repeat Ablations	16.2.17.3	

Table Number	Population	Table Title / Summary	Supporting Listing	Interim Analysis Number
14.2.6	ITT, PP	Number of New AAD Drugs per Subject	16.2.17.3	
14.2.7	ITT, PP	Summary of Dose changes	16.2.22	

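### The Kaplan-Meier analysis by number of ablations groups Test subjects at time zero by procedures done later, with no cut-off at the event, so its rates can differ when repeat ablation has no effect

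*SAP*

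**What the plan says.** The analysis is part of a named secondary endpoint (SAP 2.2.1): "Rate and time to persistent AF/AT at 1 year and 2 years, rate of persistent AF/AT by number of ablations at 3 years". SAP 10.6.1 defines the groups: "Number of ablations will be categorized into 1, 2, ≥ 3 ablations if sample sizes allow"; failing that, one against two or more. Protocol 13.12.1 has the same design: its 3-year results "will be reported for the Test Group by the number of ablations".

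Four other places bear on it.

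- **Time zero.** SAP 8.3 decides to "use date of procedure as start date for the test group, and date of randomization as start date for the control group". Every repeat ablation in the Test Group therefore falls after time zero.
- **After the event.** Protocol 11.2.1 drops the interim visits for subjects who progress, but "they will be followed for safety through the 3-years study period by their hospital". Repeat ablations are also a per-subject count with no stop at progression: "Number of repeat ablations and new anti-arrhythmic drugs (AAD) per subject throughout 3 years follow-up".
- **Cut-off rule.** SAP 7 has one for the Control Group only: "subjects from the control group who have an ablation procedure after the primary endpoint is met will not be analyzed as cross-over". No corresponding rule is given for repeat ablations in the Test Group.
- **Output.** The table title is "Time to Persistent AF/AT by Number of Repeat ablations Results of Kaplan-Meier analysis". Unlike the 1-year and 2-year tables, it names no log-rank test.

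**The concern.** A Kaplan-Meier curve needs groups that are known when the clock starts. Here they are not, and two mechanisms follow.

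- A subject re-ablated before progressing must have stayed event-free until that date. Placing the subject in the higher category from day 0 credits it with time in which no event could occur (immortal time). This makes two or more ablations look better.
- If an ablation done after progression counts, a subject who progressed after one procedure is moved, with the event, into the higher category. This makes two or more ablations look worse.

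Which mechanism dominates depends on a counting rule that the SAP does not state. At stake is whether the curves, 3-year rates and confidence intervals of a listed secondary endpoint will be read as showing a benefit or harm of repeat ablation that the grouping itself created.

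**Working it through.** **Inputs from the documents.** SAP 6 gives a 3-year progression rate of 5% under ablation, 161 subjects per arm and 10% drop-out over 3 years.

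**Assumed inputs.** The documents give no re-ablation rate. Assume 20-30% of subjects are re-ablated, evenly spread from 3 months to 1.0 or 1.5 years, independently of the progression hazard. Assume 0%, 30% or 50% of those who progress after one ablation are re-ablated later. Repeat ablation has no effect on progression, so a sound analysis should show equal rates.

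**The plan's own figure.** SAP 6 states an effect size of 1.1541. Recomputing, -ln[ln(0.95)/ln(0.85)] = -ln(0.0513/0.1625) = 1.153, so the design rates are read correctly. The plan gives no figure for the analysis by number of ablations.

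**Step 1: hazard.** -ln(0.95)/3 = 0.0171 per year.

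**Step 2: only repeats before the event count.** The mean re-ablation time is (0.25 + 1.0)/2 = 0.625 or (0.25 + 1.5)/2 = 0.875 years, which leaves 2.375 or 2.125 years at risk.

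- Rate with two or more: 1 - exp(-0.0171 × 2.375) = 4.0%; 1 - exp(-0.0171 × 2.125) = 3.6%.
- Share of subjects with two or more: 0.20 × exp(-0.0171 × 0.625) = 19.8%; 0.30 × exp(-0.0171 × 0.875) = 29.6%.
- Rate with one: (5 - 19.8 × 0.0398)/80.2 = 5.3%; (5 - 29.6 × 0.0357)/70.4 = 5.6%.

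**Step 3: repeats after the event also count.** The two extreme settings, per 100 subjects:

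- 20% re-ablated by 1.0 year, half of later progressors re-ablated. Events are 0.79 (two or more) and 4.21 (one), and 2.11 move up. Rates become (0.79 + 2.11)/(19.8 + 2.11) = 13.2% and 2.11/(80.2 - 2.11) = 2.7%.
- 30% re-ablated by 1.5 years, 30% of later progressors re-ablated. Events are 1.06 and 3.94, and 1.18 move up. Rates become (1.06 + 1.18)/(29.6 + 1.18) = 7.3% and (3.94 - 1.18)/(70.4 - 1.18) = 4.0%.

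Simulation of 2,000,000 subjects agrees: 3.6-4.0% against 5.3-5.6% in step 2, and 7.3-13.3% against 2.7-4.0% in step 3.

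**Step 4: a second model.** Re-ablation is spread over all 3 years at an assumed 10-40%, again with no effect on progression.

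| Counting rule | One | Two or more |
|---|---|---|
| Before the event only | 5.3-6.4% | 2.6-2.8% |
| All to 3 years, re-ablation hazard unchanged by the event | about 5.0% | 4.9-5.0% |
| All to 3 years, hazard 3 times higher after the event | 3.2-4.6% | 7.7-9.1% |
| All to 3 years, hazard 10 times higher after the event | 1.2-3.4% | 10.3-18.3% |
| Count updated over time | about 5.0% | 5.0-5.1% |

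The same data give a lower, equal or higher rate for two or more ablations, depending on the rule and on how progression changes re-ablation. Updating the count over time removes the artefact (hazard ratio 0.99-1.02).

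**Step 5: scale in this trial.** Expected Test Group events are 161 × 0.05 = about 8. At 20-30% re-ablated, the higher category holds 161 × 0.20 = 32 to 161 × 0.30 = 48 subjects. In step 2 its rate falls by at most 1.4 points, and 48 × 0.014 = 0.7, less than one event.

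**The case against.** The strongest reply is that this is a descriptive table. SAP 10.6.1 applies log-rank tests to the two treatment groups at 1 and 2 years, not to the ablation categories, and no alpha or claim rests on them. That stands. With about 8 events the intervals will be wide (2 events in 40 subjects gives an exact 95% interval of about 0.6-17%), and at a 5% rate no median would be reached.

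A reader might infer that the SAP counts ablations done after progression. The documents do not say so: they give no cut-off, which is different. The one rule they do give, for Control cross-over, disregards ablation after the endpoint, and a programmer could carry that principle over. Against this, follow-up continues after the event, repeat ablations are counted over 3 years, and protocol 11.4.1 requires every re-ablation to be documented. Either reading is open.

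A reader might also infer that a false difference is certain, or that the rates have no valid interpretation. Neither follows. One case in the working shows no difference, although it needs re-ablation to be unaffected by progression, which is hard to expect when re-ablation is done for recurrence (protocol 11.4.1). Rates by eventual number of procedures can be read as description, but not as the effect of the number of ablations.

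**Conclusion.** The point holds in a limited form. SAP 10.6.1 and protocol 13.12.1 group Test subjects from the index procedure by a count known only later, with no landmark or time-dependent method and no cut-off at the event. The resulting rates can differ with no true effect.

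The direction is not fixed. Counting only repeats before the event favours two or more ablations; counting later repeats reverses this if progression prompts re-ablation. The widest gap in the first model, nearly five-fold (13.2/2.7 = 4.9), is an assumed scenario and not a prediction. All sizes rest on assumed re-ablation rates and timing, and on re-ablation being independent of the progression hazard before the event.

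The primary result and type I error are not affected. The point merits a correction because this is a listed secondary endpoint with its own tables and figures, and nothing in the SAP warns against reading the curves as a comparison.

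**What to change.** Amend SAP 10.6.1 in three respects.

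1. Count only ablations before the primary-endpoint date or, if there is no event, the censoring date. This matches the rule SAP 7 already has for Control cross-over.
2. Make the count time-dependent. A subject contributes to the one-ablation risk set until the repeat-ablation date and to the higher risk set from then on, using an extended Kaplan-Meier estimate or a time-dependent Cox model. SAP 10.2 already handles cross-over in this way.
3. State that the result is descriptive and not causal. Re-ablation follows recurrence, so confounding by indication remains after the first two changes.

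Apply the same rule to the HRS 2017 version, using that definition's event date. A 12-month landmark is less suitable because it discards first-year events from a total of about 8.

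The cost is a few sentences and one counting-process dataset of the kind SAP 10.2 already needs. The downside is that the higher risk set will hold few events, so its estimates will be imprecise.

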10.6.2 Number of Repeat Ablations and New AAD Drugs

To analyze this secondary effectiveness endpoint (number of repeat ablations and new AAD drugs per subject throughout 3 years follow-up), the number of repeat ablations will be summarized and listed for the subjects who have undergone at least one ablation. In addition, new AAD use (number of new AAD drugs per subject) and the frequency of dose changes will be summarized and listed for all subjects by treatment group. A new AAD will be defined as an AAD (class I or class III, or AV nodal blocking agents such as beta blockers (BB) and calcium channel blockers (CCB), which was started after randomization and which was not administered at baseline (i.e. there is no AAD entry with the same preferred term at baseline). The analyses will be performed on both ITT and PP populations. All medications will be coded by using the World Health Organization Drug Dictionary (September 2011 or newer) for this study. The number and percentage of subjects taking new AAD medications will be summarized by ATC level 2 and ATC level 4, overall and by treatment for the ITT and PP population.

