**Schedule of Examinations**

**Table 1. Summary of Subject Assessments:**

Assessments	BL D0 	M3 D76- 104	M6 D166- 210	M9 D240 -300	Y1 D330 -420	M18 D480 -600	Y2 D630 -809	M30 D810- 989	Y3 D990- 1170	UNS
Clinic visit	X	X	X		X		X		X	X
Phone follow-up 				X		X		X		
Patient Information and Consent	X									
Medical history	X									
HATCH score	X	X	X		X		X		X	X
ECG 	X	X	X		X		X		X	X
TTM 		X	X	X	X	X	X	X	X	X
TEE 	X									
TTE 	X				X		X		X	
QoL (EQ-5D, AFEQT) 	X	X	X		X		X		X	
Health status 	X	X	X		X		X		X	X
Cardiac medication	X	X	X	X	X	X	X	X	X	X
Adverse events		X	X	X	X	X	X	X	X	X
Cardioversion / re-ablation documented		X	X	X	X	X	X	X	X	X

1. Phone follow-up calls include check for AEs, changes in cardiac medication and TTM.
2. To be collected if completed as standard of care.
3. Dispensation of TTM device at Month 3. Additional details/instructions regarding TTM monitoring are provided below.
4. Only for patients randomized to PVI, within 48 hours pre-procedure.
5. TTE to be performed within 30 days pre-treatment. For the Test Group, TTE must be repeated prior to discharge
6. AFEQT questionnaire is only to be completed by a subpopulation due to limited validated translations
7. LA Size, blood pressure, NYHA Functional Classification of heart disease, Diabetes, lipid profile, renal function and dementia.
8. Day 0 Test Group (PVI)= Index ablation procedure and Day 0 Control Group (AAD) = Randomization

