6. SAMPLE SIZE DETERMINATION

A total sample size of 322 (161:161) subjects will be required to ensure 85% power to detect the effect size measured by negative log of the hazard ratio equal to 1.1541 (treatment group over control group).

$$-\log_e \left(\frac{\hat{\lambda}_t}{\hat{\lambda}_c} \right) = -\log_e \left(\left(-\frac{\log_e(0.95)}{3} \right) / \left(-\frac{\log_e(0.85)}{3} \right) \right) = 1.1541$$

This calculation assumes a 50% cross-over rate from the AAD group to the ablation group, a 10% drop-out rate in each group over the 3 year follow-up period, and 1.5 years accrual time. This calculation is based upon one-sided superiority testing with alpha equal to 0.025. Using meta-analysis, the rates of disease progression at the end of follow-up are estimated to be 25% and 5% in the AAD and ablation group, respectively (see the point estimate justification document for details, Appendix C of the CTP). The cross-over to ablation is reflected in the use of the proportion 0.85 instead of 0.75 in the formula above. The sample size calculation is based upon the method developed by Rubinstein, Gail and Santner⁴ (RGS, 1981) and also incorporates group sequential design with multiple interim looks.

Adaptive Sample Size Re-estimation

Due to the uncertainties associated with the cross-over rate and the effect size, the sample size will be reestimated at the time of the first interim analysis. Conditional power (CP) will be calculated at that time to determine how promising the interim results are. CP is defined as the conditional probability that the final result will exceed a critical value given the data observed thus far, and the assumption that the trend to be observed in the remainder of the study⁵ will follow the expectation, which was used in the original sample size calculation. If the CP is less than 0.3, then the study is considered not promising, and the sample size will not be increased. If the CP is

greater than 0.9, then the study is deemed fully powered and the sample size will not be increased. If the CP falls in the promising zone (0.3-0.9), the sample size will be re-estimated based upon the observed effect size.

In detail, the following formula will be applied to re-estimate the sample size:

$$M = N \left(\frac{\delta}{\Delta} \right)^2$$

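### Repeat ablations per ablated subject are not adjusted for time since first ablation, so the ITT Control and pooled PP Test means are not comparable with ITT Test

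*SAP*

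**What the plan says.** **What is counted.** SAP 10.6.2 defines the endpoint as "number of repeat ablations and new AAD drugs per subject throughout 3 years follow-up". For the ablation part, "the number of repeat ablations will be summarized and listed for the subjects who have undergone at least one ablation". On populations it adds: "The analyses will be performed on both ITT and PP populations". Protocol 13.12.2 plans the same, and the output is SAP table 14.2.5. Protocol 13.16 gives the method as descriptive statistics, and no test is planned for repeat ablations.

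**Which clock applies.** Note 8 to Protocol Table 1 sets "Day 0 Test Group (PVI)= Index ablation procedure and Day 0 Control Group (AAD) = Randomization". Protocol 11.2.1 does not restart the clock at cross-over: "Subjects in the Control Group who undergo an ablation procedure (cross-over), will continue follow-up according to their initial schedule".

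**Which column a cross-over subject falls in.** In ITT, SAP 7 keeps these subjects in Control, and SAP 8.1 lays out ITT tables by randomized arm. In PP, "cross-over subjects will be included in the Test Group for PP analyses". SAP 7 applies that rule to tables that are not by visit, which covers table 14.2.5. The complete exclusion of cross-over subjects from PP concerns only by-visit summaries and repeated measurement models.

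For this table the plan has no person-time denominator, no fixed window after the first ablation, and no separate cross-over column in PP.

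**The concern.** A subject becomes at risk of a repeat ablation only at the first one. For Test subjects that moment is day 0. For cross-over subjects it comes later, while the end of observation stays at year 3 from randomization. Two groups with the same tendency to need a repeat would then show different means per ablated subject, because one was watched for less time.

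Two comparisons that readers will naturally make are affected: Test against Control within ITT, and ITT Test against PP Test.

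The SAP deals with this kind of problem elsewhere. Section 8.3 moves the Test start date to the procedure so that follow-up length matches between arms. Section 10.2 treats treatment as time-dependent for cross-over subjects. Sections 9.3, 10.3, 11.2 and 11.5 show them separately. Section 10.6.2 has no such protection for repeat ablations. Section 5.1 also records that the study was terminated early, so some subjects in either arm may not have the full 3 years.

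**Working it through.** **Figures from the plan.** The documents state no expected number of repeat ablations, so there is none to reproduce. Two design figures are used, both from SAP 6: 161 subjects per arm, and cross-over ("This calculation assumes a 50% cross-over rate from the AAD group to the ablation group"). Half of 161 is 80.5, taken as 80. The 50% agrees with the plan's own arithmetic: 0.5 × 0.75 + 0.5 × 0.95 = 0.85, the Control proportion in the hazard-ratio formula, and −ln(ln 0.95 / ln 0.85) = 1.153 against the printed 1.154.

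**Assumptions not in the documents.** The repeat hazard depends only on time since first ablation and is the same in Test and cross-over subjects. There is no drop-out. Cross-over timing and the shape of the repeat hazard are varied.

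**Formulas.** Let F(t) be the expected repeats by t years after first ablation, as a share of those by 3 years. A subject who crosses over at time c contributes F(3 − c).

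- ITT Control, relative to equal follow-up: R = mean of F(3 − c). With a constant repeat hazard, R = (3 − mean c)/3.
- PP Test, relative to equal follow-up: (161 + 80R)/241.

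**Results.** The front-loaded pattern puts 70%, 20% and 10% of repeats in years 1, 2 and 3 after ablation. With a constant cross-over hazard reaching 50% at 3 years, h = ln 2/3 = 0.231 per year, and the mean cross-over time among those crossing is 1/0.231 − 3 = 1.33 years.

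| Repeat hazard | Cross-over timing | ITT Control (R) | PP Test |
|---|---|---|---|
| Constant | All in year 1, mean 0.5 y | 2.5/3 = 0.83 | 0.945 |
| Constant | Constant hazard, mean 1.33 y | 1.67/3 = 0.56 | 0.853 |
| Constant | Uniform over 3 y, mean 1.5 y | 1.5/3 = 0.50 | (161 + 40)/241 = 0.834 |
| Front-loaded | All in year 1 | (0.90 + 1.00)/2 = 0.95 | (161 + 76)/241 = 0.983 |
| Front-loaded | Uniform over 3 y | (0.35 + 0.80 + 0.95)/3 = 0.70 | (161 + 56)/241 = 0.900 |

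The shortfall is 5-50% for ITT Control and about 2-17% for PP Test.

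**Sensitivity to the cross-over rate.** Protocol 8.3 cites 42% to 59% cross-over within 1 year in earlier studies, which would be 68 or 95 of 161. With a constant repeat hazard, PP Test then runs from (161 + 68 × 0.833)/229 = 0.951 (42%, all in year 1) to (161 + 95 × 0.50)/256 = 0.814 (59%, uniform over 3 years).

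**Mean versus total.** At an assumed 0.30 repeats per subject over 3 years, Test contributes 161 × 0.30 = 48.3. With uniform cross-over, cross-over subjects add 80 × 0.15 = 12. The PP Test total rises to 60.3, while the mean falls from 0.30 to 60.3/241 = 0.25.

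**Break-even.** With constant hazards, a cross-over repeat rate of 1/0.83 = 1.2 times the Test rate (all in year 1) to 1/0.50 = 2.0 times (uniform) cancels the shortfall.

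**Check of a per-patient-year rate.** With front-loaded repeats and uniform cross-over, cross-over subjects have 70% of the repeats in 50% of the time. Their rate is 0.70/0.50 = 1.4 times the Test rate, although the hazard after ablation is identical.

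**The case against.** The strongest case on the other side is that nothing is miscounted. The endpoint is a count within study follow-up, and by that definition it is right. The documents set no target of 3 years after first ablation. This stands: a reader might infer that the counts themselves are too low, but only the mean per ablated subject falls short, and only against equal follow-up. The PP Test total goes up when cross-over subjects are added.

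Second, a reader might infer that the table would show late ablation needing fewer repeats than early ablation. The documents do not support that. It requires similar repeat rates, and Appendix B of the protocol says cross-over subjects cannot be assumed to resemble either randomized group; it suggests they may be older, with higher HATCH scores. A higher repeat rate among them could cancel or reverse the shortfall.

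Third, ITT already keeps cross-over subjects apart from Test, and the ITT Test column is unaffected. SAP 10.6.2 mentions treatment groups only for drug use, so the ITT Control column for repeats is inferred from the general rule in SAP 8.1. This stands in part: separate columns do not equalize time at risk, and PP has no separation.

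Fourth, the size rests on inputs the documents do not supply, and the 1-year cross-over figures in Protocol 8.3 point towards early cross-over and a smaller effect. This also stands, which is why only a range is given.

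**Conclusion.** The point holds as a matter of comparability. The ITT Control and PP Test means rest on less time at risk than the ITT Test mean, by design, and the plan does not adjust for it. Under equal repeat hazards and the plan's 50% cross-over, the shortfall lies between a few percent and one half for ITT Control, and between about one fiftieth and one sixth for PP Test. Where it falls depends on cross-over timing and on how early repeats cluster after an ablation. The sign of the difference that will be observed cannot be predicted.

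The consequence is limited. This is a named secondary endpoint, but it is descriptive. The trial's objective compares ablation with drug therapy for AF progression, not early with late ablation. Alpha, power and the primary result are untouched. The defect is that, with unequal exposure and selection possibly working in opposite directions, the unadjusted means cannot be interpreted side by side.

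**What to change.** In SAP 10.6.2 and table 14.2.5:

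- Add a Kaplan-Meier estimate of time from first ablation to first repeat ablation, censored at last follow-up. This handles unequal follow-up without assuming a constant repeat hazard, and it also accommodates follow-up cut short by early termination.
- Show Test index-ablation and cross-over subjects in separate columns in PP as well as ITT.
- Keep the raw counts, labelled as counts within study follow-up.
- Do not rely on a per-patient-year rate alone, since it is comparable only if the repeat hazard is constant.
- State whether Control subjects first ablated after reaching the primary endpoint enter the table. They have had an ablation, but SAP 7 does not analyze them as cross-over.

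The cost is one derived variable (time from first ablation) and one more summary. Ablation procedures are already listed (listing 16.2.15), and the Cox model in SAP 10.2 already needs the time of cross-over.
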